6.1.3 Trametinib Dose Modifications for Visual Changes

Trametinib is known to be associated with visual adverse events. An ophthalmologist should be consulted if changes in vision develop. However, if the visual changes are clearly unrelated to study treatment (e.g., allergic conjunctivitis), then monitor closely as it may be reasonable to defer ophthalmic examination. Special attention should be given to retinal findings (e.g., retinal pigment epithelial detachment (RPED) or retinovascular abnormalities (i.e., branch or central retinal vein occlusions [RVO]).

The ophthalmology exam will include best corrected visual acuity, visual field examination, tonometry, slit lamp biomicroscopic examination, and indirect fundoscopy. Optical coherence tomography is recommended at scheduled visits and if retinal abnormalities are suspected. Other types of ancillary testing including visual field examination, fundus photography, and fluorescein angiography may also be indicated as determined by clinical exam.

Guidelines regarding event management and dose reduction for visual changes considered to be related to study treatment are provided in the table below.

Management and Trametinib Dose Modification for Visual Changes and/or Ophthalmic Examination Findings		
Event CTCAE Grade	Management Guideline	Dose Modification
Grade 1*	
 Consult ophthalmologist within 7 days of onset. 	
 If dilated fundus examination cannot be performed within 7 days of onset, hold trametinib until RPED and RVO can be excluded by retina specialist/ophthalmologist. If RPED and RVO excluded, continue/or restart trametinib at same dose level. If RPED suspected/diagnosed: See RPED dose modification table below (following this table); report as SAE. If RVO diagnosed: Permanently discontinue trametinib and report as SAE.
Grade 2 and Grade 3	
 Consult ophthalmologist immediately. 	
 Hold trametinib If RPED or RVO excluded, restart trametinib at same dose level after visual AE is \leq grade 1. If no recovery within 3 weeks, discontinue trametinib If RPED diagnosed: See RPED dose modification table below; report as SAE. If RVO: Permanently discontinue trametinib and report as SAE.
Grade 4	
 Consult ophthalmologist immediately. Report as SAE. 	
 Hold Trametinib If RPED/RVO excluded, may restart trametinib at same or reduced dose after discussion with the CTEP Medical Monitor. If RVO or RPED, permanently discontinue trametinib.

Abbreviations: RPED = retinal pigment epithelial detachments; RVO = retinal vein occlusion; SAE = serious adverse event
 *If visual changes are clearly unrelated to study treatment (e.g., allergic conjunctivitis), monitor closely but ophthalmic examination is not required.

Trametinib Dose Modification for RPED	
Event CTCAE Grade	Action and Dose Modification
Grade 1 RPED (Asymptomatic; clinical or diagnostic observations only)	
 Continue treatment with retinal evaluation monthly until resolution. If RPED worsens, follow instructions below.
Grade 2-3 RPED (Symptomatic with mild to moderate decrease in visual acuity; limiting instrumental ADL)	
 Interrupt trametinib. Retinal evaluation monthly. If improved to \leq Grade 1, restart trametinib with one dose level reduction (reduced by 0.5 mg) or discontinue in patients taking trametinib 1 mg daily. If no recovery within 4 weeks permanently discontinue trametinib

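### Section 6.1.3: the grade 2-3 visual-changes row should require RPED and RVO both to be excluded before restart, as the grade 1 row does (editorial)

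*Combined protocol and SAP*

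**What the plan says.** All of the text is in section 6.1.3, in the table on visual changes and ophthalmic findings.

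- **Grade 1 row.** If a dilated fundus examination cannot be done within 7 days, the site must "hold trametinib until RPED and RVO can be excluded by retina specialist/ophthalmologist". Then: "If RPED and RVO excluded, continue/or restart trametinib at same dose level". Both instructions use *and*.
- **Grade 2-3 row.** The management column says "Consult ophthalmologist immediately", and the dose column starts with a hold. The restart instruction is "If RPED or RVO excluded, restart trametinib at same dose level after visual AE is" grade 1 or lower. A further bullet adds "If no recovery within 3 weeks, discontinue trametinib". Two more bullets deal with confirmed disease. One opens "If RPED diagnosed" and sends the site to the separate RPED table; the other says, for RVO, "Permanently discontinue trametinib and report as SAE".
- **Grade 4 row.** Restart is possible if the two conditions, written with a slash between them, are excluded, and only after discussion with the CTEP Medical Monitor. The next bullet stops drug permanently for either diagnosis.

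**The concern.** The restart test for the more severe event is, on its literal wording, weaker than the test for the milder one. That cannot be intended. This is an operative dosing instruction, and at grades 2-3 the site applies it without the Medical Monitor discussion that grade 4 requires.

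At stake is a patient whose vision has returned to grade 1 or better while the cause is only half settled. If RPED has been ruled out and RVO has not, the literal wording lifts the hold and returns the patient to the same dose, although a confirmed RVO would end treatment for good. In the mirror case, with RVO ruled out and RPED open, the patient also restarts at the same dose. The RPED table would require one dose level less for grade 2-3 RPED, or discontinuation at 1 mg daily.

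**Working it through.** The plan gives no figure to reproduce here. The check compares the rows and then counts work-up states.

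**1. Conjunction by row**

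| Row | Joining word in the restart condition | What follows if either is diagnosed |
|---|---|---|
| Grade 1 | *and* (also in the hold rule) | RPED suspected or diagnosed: RPED table. RVO: permanent stop |
| Grade 2-3 | *or* | RPED diagnosed: RPED table. RVO: permanent stop |
| Grade 4 | slash | Permanent stop for either |

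The grade 2-3 row is the only one that uses *or* in the restart condition.

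**2. States of the work-up**

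Let each condition be excluded, unresolved or diagnosed, giving 3 × 3 = 9 combinations.

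- Restart wording met under *and*: 1 (both excluded).
- Restart wording met under a literal *or*: 3 (RPED excluded, any RVO status) + 3 (RVO excluded, any RPED status) − 1 (counted twice) = 5.
- Extra states admitted by *or*: 5 − 1 = 4.

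**3. Which extra states other bullets catch**

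| RPED | RVO | Other bullet in the row that applies |
|---|---|---|
| Excluded | Diagnosed | RVO bullet: permanent stop |
| Diagnosed | Excluded | RPED bullet: RPED table |
| Excluded | Unresolved | None |
| Unresolved | Excluded | None |

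So 4 − 2 = 2 states are left uncovered. The 3-week stop does not close them, because it is triggered by lack of recovery and these patients have recovered. Nor does the RPED bullet: at grades 2-3 it covers diagnosed RPED only, whereas the grade 1 row also covers suspected RPED.

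**4. Can an uncovered state arise?**

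Section 6.1.3 makes indirect fundoscopy part of the standard examination. Footnote d of the study calendar (section 10) places optical coherence tomography and fundoscopy in the same ophthalmology exam. Those two should therefore normally report together. Section 6.1.3 leaves ancillary tests, including fluorescein angiography, to be ordered on the clinical findings. The plausible open state is therefore RPED excluded at the exam with angiography for RVO still to come. That angiography would be ordered for RVO is an assumption; the protocol does not tie the test to one condition.

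**5. Bound on RVO cases**

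The adverse event list in section 7.1 places RVO in its rare category, below 3%. With the target of 27 fusion-positive patients, expected RVO cases of any kind are below 27 × 0.03 = 0.81. Enrolment will exceed 27 because fusion-negative and untested cases are replaced; assuming 40 patients, the bound is 40 × 0.03 = 1.2. Only some of these would pass through the open state, and the documents give no rate for that.

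**The case against.** The best reply is that nobody would misread the row. In ordinary English the phrase means that neither condition is present, and the bullets beneath it show what happens when one is. Drug is held, a specialist is consulted immediately, and recovery to grade 1 or lower is required. RVO is rare, and criterion 3.2.9 excludes patients with a history of it or current evidence or risk of it. Fundoscopy and tomography belong to one exam, so a split result is an inference, not a pathway that the protocol sets out.

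Most of this stands, and it is why the point is editorial. It does not remove the mismatch: the authors wrote *and* twice one row earlier, and the unresolved state has no bullet of its own.

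A further reply is that the slash in the grade 4 row is just as ambiguous, so either both rows are faulty or neither is. But the grade 4 row stops drug for either diagnosis and requires discussion with the Medical Monitor before restart. The grade 2-3 row lacks that second check.

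A reader might infer that the row lets a patient with diagnosed RVO go back on drug. It does not; the row's RVO bullet requires permanent discontinuation. A reader might also infer a measurable overdose or a bias in the trial's results. The documents support neither. Any dose difference depends on a work-up being open and then turning out positive, and no frequency is given for either step.

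**Conclusion.** The wording is wrong as written and the correction is not in doubt. The consequence is minor. Two of nine logical work-up states are left without proper cover, and RVO unresolved is the more serious because a confirmed RVO ends treatment. No number of affected patients can be estimated; the expected number of RVO cases of any kind is below about one in a trial of this size, on the rare-event category and the enrolment assumption used above.

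The conclusion rests on two assumptions: that a site might apply the bullet literally, and that an ancillary test can be outstanding when vision has already recovered. If neither occurs, the current text leads to the right action. Response rate, sample size and analysis populations are unaffected either way. Confidence is high in the textual mismatch, and only modest that it would ever change a patient's treatment.

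**What to change.** In the grade 2-3 row of the visual-changes table, change *or* to *and* so that the restart condition requires RPED and RVO both to be excluded. The rest of the row can stay as it is.

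Optionally, replace the slash in the grade 4 row with *and* for consistency; its meaning is already clear from the bullet that follows and the Medical Monitor step.

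The cost is one word in one table cell, or two cells if grade 4 is aligned. It adds no procedure or visit, loosens no safeguard, and can go into the next amendment.

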6.1.1 Trametinib Dose Modification for Toxicities Not Specified in Subsequent Sections

Trametinib Treatment Modification for Clinically Significant Toxicities Deemed Related to Trametinib (This section is not for specific AEs such as hypertension, rash, ejection fraction changes, pneumonitis, diarrhea, liver chemistry, QTc prolongation, or visual changes. Refer to other sections for these specific AEs).		
CTCAE v5 Grade	Management Guideline	Dose Modification
Grade 1	Monitor as clinically indicated.	Continue trametinib at current dose level.
Grade 2 (tolerable)	Provide supportive care according to institutional standards.	
• Interrupt treatment until resolution to grade 1 or baseline.• Upon resolution, restart treatment at current dose level.
Grade 2 (intolerable) and Grade 3		
• Interrupt treatment until resolution to grade 1 or baseline.• Upon resolution to baseline or grade 1, restart with one level of dose reduction.• If the Grade 3 toxicity recurs, interrupt trametinib; When toxicity resolves to Grade 1 or baseline, restart trametinib reduced by another dose level.
Grade 4		If event resolves to grade 1 or baseline discuss potential continuation of trametinib with Medical Monitor; if continuation of treatment agreed then restart trametinib at dose reduced by one dose level . If event does not resolve, permanently discontinue trametinib.
Trametinib should be discontinued if treatment delay is ≥ 21 days due to toxicities. If the investigator concludes that continued trametinib will benefit a patient, the study chair and CTEP Medical Monitor may be consulted for the possibility of resuming trametinib, provided that toxicities have resolved to baseline or grade 1.		

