Grade 1	
 Initiate prophylactic and symptomatic treatment measures.¹ Use moderate strength topical steroid.² Reassess after 2 weeks. 	
 Continue trametinib. If rash does not recover to baseline within 2 weeks despite best supportive care, reduce trametinib by one dose level.³

Trametinib Dose Modification Guidelines and Management for Rash		
Rash Severity	Management Guideline	Dose Modification
Grade 2	
 Initiate prophylactic and symptomatic treatment measures.¹ Use moderate strength topical steroid.² Reassess after 2 weeks. 	
 Reduce trametinib by one dose level. If rash recovers to \leq grade 1 within 2 weeks, increase dose to previous dose level. If no recovery to \leq grade 1 within 2 weeks, interrupt trametinib until recovery to \leq grade 1. Restart trametinib at reduced dose level.³
Grade \geq3	
 Use moderate strength topical steroids PLUS oral methylprednisolone dose pack.² Consult dermatologist. 	
 Interrupt trametinib until rash recovers to \leq grade 1. Restart with trametinib reduced by one dose level.^{3,4} If no recovery to \leq grade 2 within 4 weeks, permanently discontinue trametinib.

1. Rash prophylaxis is recommended for the first 6 weeks of study treatment.
 2. Moderate-strength topical steroids: Hydrocortisone 2.5% cream or fluticasone propionate 0.5% cream.
 3. Approval of CTEP Medical Monitor is required to restart study treatment after >4 weeks of interruption.
 4. Trametinib may be escalated to previous dose level if no rash is evident 4 weeks after restarting study treatment.

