Uncomplicated Diarrhea,¹ Grade 3 or 4 Any Complicated Diarrhea²	
 Clinical evaluation mandatory. Loperamide³: Initially 4 mg, followed by 2 mg every 4 hours or after every unformed stool; maximum 16 mg/day. Continue until diarrhea-free for 12 hours. Oral antibiotics and second-line therapies if clinically indicated. Hydration: Intravenous fluids if clinically indicated. Antibiotics (oral or intravenous) if clinically indicated. Intervention should be continued until the subject is diarrhea-free for \geq24 hours. Intervention may require hospitalization for subjects at risk of life-threatening complications. 	
 Interrupt trametinib until diarrhea resolves to \leq grade 1. Restart with trametinib reduced by one dose level.⁴ If 3 dose reductions of study treatment are clinically indicated, permanently discontinue trametinib. If treatment delay is >4 weeks, discontinue trametinib.

1. **Uncomplicated diarrhea** defined by the absence of symptoms such as cramping, nausea/vomiting, \geq grade 2, decreased performance status, pyrexia, sepsis, neutropenia \geq grade 3, frank bleeding, and/or dehydration requiring intravenous fluid substitution.

2. **Complicated diarrhea** defined by the presence of symptoms such as cramping, nausea/vomiting, \geq grade 2, decreased performance status, pyrexia, sepsis, neutropenia \geq grade 3, frank bleeding, and/or dehydration requiring intravenous fluid substitution.

3. Loperamide should be made available prior to start of study treatment so loperamide administration can begin at the first signs of diarrhea.

4. Escalation of trametinib to previous dose level is allowed after consultation with the medical monitor and in the absence of another episode of complicated or severe diarrhea in the 4 weeks subsequent to dose reduction.

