6.1.6 Trametinib Dose Modification for Pneumonitis

Pneumonitis has been observed in patients receiving trametinib. To reduce the risk of pneumonitis, patients will be monitored closely for symptoms and evaluated with imaging and functional tests. Dose modification and supportive care guidelines for pneumonitis are described in the tables below.

Pneumonitis Guidelines for Trametinib Monotherapy		
CTCAE Grade	Adverse Event Management	Action and Dose Modification
Grade 1	
 • CT scan (high-resolution with lung windows) recommended. • Work-up for infection • Monitoring of oxygenation via pulse-oximetry recommended • Consultation with pulmonologist recommended 	
 • Continue trametinib at current dose
Grade 2	
 • CT scan (high-resolution with lung windows) recommended. • Work-up for infection • Consult pulmonologist • Pulmonary function tests – if < normal, repeat every 8 weeks until \geq normal • Bronchoscopy with biopsy and/or BAL recommended • Symptomatic therapy including corticosteroids if clinically indicated 	
 • Permanently discontinue trametinib if pneumonitis is related to treatment.
Grade 3	
 • Same as grade 2 	
 • Permanently discontinue trametinib
Grade 4	
 • Same as grade 2 	
 • Permanently discontinue trametinib

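### Once RPED and RVO are excluded, the grade 4 visual row allows trametinib to restart with no written recovery condition, although the milder grade 2-3 row has one

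*Combined protocol and SAP*

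**What the plan says.** The visual-changes table in section 6.1.3 covers events considered related to treatment.

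- **Grade 4 row.** Consult an ophthalmologist immediately, report as an SAE and hold trametinib. Then: "If RPED/RVO excluded, may restart trametinib at same or reduced dose", once there has been "discussion with the CTEP Medical Monitor. If RVO or RPED, permanently discontinue trametinib". The permanent stop for RVO or RPED is therefore in the same cell as the restart option. The restart option names no grade to which the event must first improve.
- **Grade 2 and 3 row.** Consult immediately and hold. Then: "If RPED or RVO excluded, restart trametinib at same dose level after visual AE is" grade 1 or less, with discontinuation if there is no recovery within 3 weeks.

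The general grade 4 rule in section 6.1.1 puts recovery first: "If event resolves to grade 1 or baseline discuss potential continuation of trametinib with Medical Monitor". The table that holds this rule lists visual changes among the events it does not cover.

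**The concern.** The written rule is looser for the worse event. After a grade 2 or 3 visual event a site must wait for grade 1 or less. After a grade 4 event with RPED and RVO excluded, the text asks for a conversation with the monitor and nothing more about the state of the eye. The general rule cannot fill the gap, because section 6.1.1 excludes visual changes.

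What is at stake is rechallenge, possibly at full dose, of a patient whose treatment-related grade 4 visual event has not resolved, without any breach of the protocol as written.

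**Working it through.** The plan gives no figure of its own on this point. The check has two parts: a comparison of rows, and a rough count of the patients it could reach.

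**Rows in section 6.1 that cover CTCAE grade 4**

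| Section | Row | Rule before any restart |
|---|---|---|
| 6.1.1 | Unspecified toxicities, grade 4 | Recovery: "If event resolves to grade 1 or baseline discuss potential continuation of trametinib with Medical Monitor" |
| 6.1.2 | Rash, grade 3 or higher | Recovery: "Interrupt trametinib until rash recovers to" grade 1 or less |
| 6.1.3 | Visual, grade 4 | RPED/RVO excluded and monitor discussion; no recovery grade |
| 6.1.4 | Diarrhea, grade 3 or 4 (same row also covers any complicated diarrhea) | Recovery: "Interrupt trametinib until diarrhea resolves to" grade 1 or less |
| 6.1.6 | Pneumonitis, grade 4 | No restart: "Permanently discontinue trametinib" |
| 6.1.7 | Symptomatic LVEF decrease, grade 3 or 4 | No restart: permanent stop |

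Count: 3 recovery first + 2 permanent stop + 1 restart path without a recovery condition = 6. The rash, diarrhea and LVEF rows are shared with grade 3; three rows (6.1.1, 6.1.3, 6.1.6) are labelled grade 4 alone.

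**How monitor input is used elsewhere.** In several places it comes on top of recovery. Section 6.1.1 does this for grade 4, and again for delays of 21 days or more, where it allows the "possibility of resuming trametinib, provided that toxicities have resolved to baseline or grade 1". Section 6.1.7 does it for asymptomatic LVEF decrease, and section 6.1.8 for QTc prolongation.

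**Which grade governs.** The documents do not say whether a row follows the worst grade reached or the current grade.

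- Worst grade: restart at any point before recovery is permitted.
- Current grade: an event that improves to grade 2 or 3 moves to the row that requires grade 1 or less, and the gap is only restart while still grade 4.

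**How many patients**

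1. Treated patients. Section 13.1 requires 27 fusion-positive patients and reports 3 negative and 1 untestable tumor in stage I (13 patients). If no more occur: 27 + 4 = 31. If the stage I rate persists: 27 / (9/13) = 39.
2. Denominator. Section 2.2.1.3 reports one grade 4 visual disorder at 2 mg monotherapy across five trials, without the pooled number treated. Diarrhea affected about 320 patients, at 33% to 58% by trial, so the pooled number lies between 320/0.58 = 552 and 320/0.33 = 970. This assumes that the diarrhea and visual figures come from the same five trials. The range sits inside those implied by the visual figures (85/0.21 = 405 to 85/0.04 = 2125) and the rash figures (370/0.78 = 474 to 370/0.27 = 1370).
3. Rate: 1/970 = 0.10% to 1/552 = 0.18%.
4. Expected events: 31/970 = 0.032 to 39/552 = 0.071.
5. Chance of at least one: 1 - (1 - 1/970)^31 = 3.1% to 1 - (1 - 1/552)^39 = 6.8%.
6. Uncertainty from a single event. Exact 95% Poisson limits for a count of 1 are 0.0253 and 5.572, so the expected number runs from 31 × 0.0253/970 = 0.0008 to 39 × 5.572/552 = 0.39.
7. Without the same-trials assumption, using the visual figures alone: 31/2125 = 0.015 to 39/405 = 0.096.

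These counts cover grade 4 visual events of any cause. The branch at issue covers only treatment-related events with RPED and RVO excluded, so its own number is smaller and may be zero. The documents give no basis for the share that would be restarted unresolved, so none is estimated.

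**The case against.** The strongest reply is that the decision is already controlled, by a different means. The table is offered as guidance, restart is optional, and it comes only after a hold, an urgent ophthalmology review, an SAE report, exclusion of RPED and RVO, and a monitor discussion. The grade 2-3 row has a numerical threshold but no monitor. Section 5.5 lets the investigator stop treatment on judgment, and section 12.1 provides monthly review calls. On this view, preferring a fixed grade to case review is a drafting choice. This stands in part: the safeguards are real, and a monitor may well insist on recovery. None of them sets a recovery grade, however, and elsewhere the protocol asks for recovery as well as monitor input.

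Three stronger readings are tempting, and the documents do not support them.

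- A reader might infer that the row has no permanent stop at all. It has one, for RVO or RPED, in the same cell.
- A reader might infer that nowhere else in section 6.1 can treatment resume without a stated recovery grade. The liver table in 6.1.5, which is not keyed to CTCAE grade, allows monitor-approved rechallenge without one, although its default is immediate discontinuation and it asks for approval, not just discussion. The rash section also leaves room for clinical judgment. Discretion as such is not the fault.
- A reader might infer that full-dose rechallenge before recovery is plainly authorized. That follows only if the row tracks the worst grade. On the current-grade reading the gap is much narrower, though it does not close.

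**Conclusion.** The point holds as a minor, cheap safety improvement. With RPED and RVO excluded, the grade 4 visual row permits restart at the same or a reduced dose after a monitor discussion, with no written recovery condition. The milder row has such a condition, and the other five grade 4 rows either require recovery or stop treatment for good.

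The practical reach is very small: about 0.03 to 0.07 expected grade 4 visual events of any cause in the whole trial, and possibly none in this branch. That estimate depends on one prior event and the same-trials assumption about the denominator. How much the missing condition matters also depends on the unsettled question of worst versus current grade. Sample size, error rates, ORR, PFS and OS are untouched.

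**What to change.** Amend the restart line of the grade 4 row in section 6.1.3 along these lines: where both RPED and RVO have been ruled out, treatment may resume at the previous or a lower dose only when the visual event has returned to grade 1 or less, or to baseline, and the case has been discussed with the CTEP Medical Monitor. The other instructions in the row stay as they are. This also settles the worst-grade or current-grade question for this row, since either reading then requires recovery.

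No limit on the length of the hold is needed. In particular, the absolute 3-week stop of the grade 2-3 row should not be copied across, so that a late restart after recovery remains possible.

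The cost is one table-row edit in a protocol amendment, with no added visits, tests or patients. The only loss is the monitor's discretion to agree to a restart before recovery.
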